## 8.17. Metabolic markers

Random plasma/blood glucose and OGTT tests will be used for the diagnosis of diabetes according to the recommendations by WHO and the American Diabetes Association.

## 8.17.1. Random plasma/blood glucose

Random plasma/blood glucose tests will be conducted on every visit for every child that has tested positive for any islet cell autoantibodies.

A clinical center may stop doing random glucose measurements on a subject who meets the following criteria:

There has been only 1 positive antibody sample in the child's life (excluding maternal transfer of autoantibodies)

## AND

There have been 2 consecutive negative antibody samples after the positive.

## 8.17.2. OGTT (Oral Glucose Tolerance Test)

Oral Glucose tolerance test (OGTT) tests will be performed every six months on every child who has tested positive for two or more autoantibodies (GADA, IAA, IA-2A, ZnT8A), regardless of autoantibody positivity confirmation or persistence, at any previous visit (but both antibodies must be positive at the same visit) and is three years of age or older. Oral glucose is administered in a dose of 1.75 g/kg body weight to a maximum of 75 grams in children, as a solution in flavored water, consumed within 5 minutes. A six-time point OGTT is performed with venous samples at -10, 0, 30, 60, 90, 120 minutes, which includes sampling for glucose, insulin and C-peptide at all time-points. Glucose will be measured locally. All samples will be shipped to the OGTT laboratory for processing.

Children who are not willing to participate in a six-time point OGTT can complete the original two-time point protocol instead: A two-time point OGTT is performed with venous glucose at time 0 minutes (for rare cases when it is not possible to obtain a venous sample from the subject, a capillary glucose at 0 minutes is acceptable) and capillary glucose at 120 minutes (if venous blood is available at 120 minutes then venous blood should be used instead of capillary blood). Glucose will be measured locally. Samples for glucose, insulin and Cpeptide will be collected at time 0 minutes and if a venous sample is collected

glucose, insulin and C-peptide samples will also be collected at time 120 minutes; all samples will be shipped to the OGTT laboratory for processing.

## 9. Outcome measures

## 9.1. Autoantibodies

The first primary endpoint of TEDDY will be the first appearance of **persistent**, **confirmed positive** anti-islet autoantibodies. It is likely that this endpoint will be relatively uncommon (many more individuals negative) and important to be rigorously defined for all the environmental evaluations and thus the following classification errors on side of rigidly defining positivity (indeterminants count as negative). An additional complication will be the potential for transplacental autoantibodies in the study cohort.

[figure not shown]
There will be two TEDDY Central Autoantibody Laboratories, one in the United States and one in Europe. All samples identified as positive in one central laboratory will be sent to the alternative central laboratory and the following criteria used for classification of samples:

Pos/Pos: If both laboratories report the sample as positive it will be classified as **confirmed positive**.

[figure not shown]
Pos/Neg discrepant samples will be classified as **indeterminate**. Samples reported as negative in the central laboratory will be classified as **negative**.

A proportion (5%) of samples reported as negative in the central laboratory will be randomly identified by the Data Coordinating Center and also sent to the alternate central laboratory for quality control purposes only. If there are significant discrepancies between the two reference laboratories, an ad hoc investigatory committee will determine what measures will be taken to improve concordance.

Schema 4: Autoantibody Confirmation Testing

For classification of individuals, **Persistent confirmed positive** is the major endpoint.

**Persistent confirmed positive** is defined as:

a. >=1 Autoantibody **Confirmed Positive** Autoantibody reacting with GADA, IAA, or IA-2A referring to a single sample and same specific autoantibodies have to be "confirmed" in the reference laboratories.

And **Persistent** (b, and c below) – refers to time sequence and the specific autoantibodies not important (for b), rather the presence of >=1 confirmed autoantibody on subsequent samples.

b. >=1 Confirmed Autoantibody positive on the next **sequential** serum sample or **diabetes** diagnosed

And

c. If sample drawn at less than 18 months of age there must be a prior sample negative for one or more autoantibodies confirmed positive or the cord blood/ mother negative for this autoantibody.

Individuals with confirmed positive autoantibodies who do not fulfill b, c and d will be classified as:

- 1. **Transient confirmed positive** if autoantibodies negative on follow-up and diabetes has not developed.
- 2. **Confirmed positive/not retested** for those without a follow-up sample.
- 3. **Potential Transplacental autoantibody** if cord blood or mother at time of birth has only autoantibody detected as confirmed positive (and no negative preceding sample in child)

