#### **OUTCOME MEASURES:**

- **First Primary Outcome:** appearance of one or more islet cell autoantibodies: GADA, IAA, or IA-2A confirmed at two consecutive visits.
- Second Primary Outcome: development of T1DM

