#### 8.2.1. Follow-up schedule

Children with increased genetic risk will be followed for environmental exposures and diet with a clinic visit every three months for the first 4 years of life. At 4 years of age and beyond those children who have been deemed persistent autoantibody positive will follow a three month visit schedule (confirmation results from the confirmatory Autoantibody lab will not be taken into

consideration for determining the subject's visit schedule, only the local lab's results will be used for this); all other subjects will attend biannual clinic visits beginning at 4 years of age until age 15. For subjects who become autoantibody positive at 4 years of age or older, the subject will be reinstated on the three month visit schedule at the first indication of autoantibody positivity and will stay on if persistent. If the next available sample is negative, thus the subject is not deemed persistent autoantibody positive, the subject will be placed on the biannual visit schedule from that point on. Subjects who have been persistently single autoantibody positive, but who become negative to all antibodies for 1 year or more will be placed on the biannual visit schedule after 4 years of age. Subjects who have been persistently multiple autoantibody positive, but who become negative to all antibodies for 1 year or more will remain on the three month visit schedule. Stool samples will be collected to assess viral exposures at monthly intervals for the first 4 years of life and then every three months until 10 years of age and then biannually after 10 years of age; it was decided to stop all stool sample collections on all subjects in August 2018 (Stool sample collection was less than 20% in Europe and 15% in the US. The small numbers did not warrant the cost of collection, processing, nor the burden on the families).

The following provides specifications for the implementation:

Before and leading up to the age of 4 years, if a child has been:

- Persistent autoantibody positive before the age of 4 years and is still autoantibody positive he/she will remain on a three month visit schedule after 4 years of age.
- Persistent single autoantibody positive before the age of 4 years, but has been autoantibody negative for 1 year leading up to the age of 4 years, the subject will switch to the biannual schedule at 4 years of age.

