# 8.12.4.3.1. Parents' distress (anxiety and depression) in response to infant's at-risk status

The 20-item State portion of the State-Trait Anxiety Inventory (STAI) (Spielberger et al., 1970) is a reliable assessment instrument for assessing situation-specific anxiety in the U.S. and internationally. It has been used in several studies assessing anxiety in islet cell antibody positive (ICA+) children and adults and their family members (Johnson et al., 1990; Roth et al., 1994; Johnson and Tercyack, 1995; Roth et al., 1996; Johnson and Carmichael, 2000; [name] et al., submitted). It has also been used to assess anxiety in mothers after they were told their infant was genetically at-risk for type 1 diabetes in PANDA (Prospective Assessment in Newborns of Diabetes Autoimmunity) (Carmichaelet al., 2003; Johnson et al., 2004) and BABY DIAB ([name] et al., submitted). We propose to use a 6-item short form of this instrument in the self-completed questionnaire filled out prior to the initial 3-month clinic visit as well as at the 6-, 15-, and 27-month visits. In a sample of over 400 PANDA mothers, whose infants were genetically at-risk for diabetes, the six-item short form correlated highly with the STAI full scale (r = .95) and showed excellent internal consistency ( $\alpha = .92$ ).

In addition, at any time during the study, should a child show evidence of persistent autoimmunity (a positive autoantibody test result on two consecutive occasions), parental reactions to the news of the child's increased diabetes risk will be assessed using the 6 item short form STAI at the child's next clinic visit. Although there is a small literature assessing the initial impact of telling a mother that her child is at increased risk for TIDM, there are no longitudinal studies assessing the impact of learning a genetically at-risk child is showing evidence of further progression toward diabetes.

At the 6-month clinic visit, parental depression will be assessed by the Edinburgh Postnatal Depression Scale administered as part of the selfcompleted questionnaire. In a recent study of 192 PANDA mothers with

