## 9.2. Diabetes

The second primary outcome of the TEDDY study will be the development of T1DM. Diabetes will be defined using the ADA Expert committee classification (Expert Committee on the Diagnosis of Diabetes Mellitus, 1997). This classification is based on pathogenesis rather than the requirement for insulin therapy.

The most common form of childhood diabetes is type 1A diabetes, caused by the autoimmune destruction of pancreatic islet beta cells leading to an absolute deficiency of insulin and marked by the presence of at least one of the islet autoantibodies described in the previous section. It is expected that by age 15 years, type 1A diabetes will develop in up to 380 children enrolled in the TEDDY follow-up study.

The HLA eligibility criteria and family history of type 1 diabetes make it unlikely that other forms of diabetes will be observed. However, it is possible that some children will progress to diabetes without an identifiable period of islet autoantibody positivity.

Recently, increased numbers of children with diabetes presenting with clinical characteristics of type 2 diabetes (typically considered a disease of adults) have been reported, especially in minority populations (American Diabetes Association, 2000). Other categories of specific disorders, (onset usually during childhood) include mitochondrial mutations and various forms of Maturity Onset Diabetes of Youth (MODY), characterized by mild to severe insulin deficiency (Hattersley, 2000;Owen et al., 2003). In addition, a form of diabetes termed "atypical diabetes mellitus in adolescents" is being reported to occur in approximately 10% of African Americans and is associated with episodes of ketoacidosis followed by disease remissions where insulin therapy is not required to prevent ketoacidosis (Winter et al., 1987).

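### The first primary endpoint has two definitions, and under Protocol 9.1 as written a later diabetes diagnosis can turn a transient positive into an autoimmunity event

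*Protocol*

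**What the plan says.** The outcome measures in the Introduction define the first primary outcome by autoantibodies "GADA, IAA, or IA-2A confirmed at two consecutive visits". No alternative is given.

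Section 9.1 opens with "The first primary endpoint of TEDDY will be the first appearance of" persistent, confirmed positive autoantibodies. It requires a confirmed positive sample (criterion a), then criterion b, ">=1 Confirmed Autoantibody positive on the next sequential serum sample or diabetes diagnosed", and, for samples drawn before 18 months of age, criterion c on transplacental antibodies. The line that introduces b and c explains persistence as "rather the presence of >=1 confirmed autoantibody on subsequent samples" and does not mention diabetes.

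Section 9.1 then classifies children who have a confirmed positive but do not meet the definition. A child is transient "if autoantibodies negative on follow-up and diabetes has not developed". Children with no follow-up sample form a separate class. The lead-in to this list refers to a criterion d, but the definition above it stops at c.

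Two other sections describe persistence by consecutive samples only. Section 8.2.1, on visit scheduling and using local laboratory results, says "If the next available sample is negative, thus the subject is not deemed persistent autoantibody positive". Section 8.12.4.3.1 describes it as "a positive autoantibody test result on two consecutive occasions".

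Section 9.2 states: "The second primary outcome of the TEDDY study will be the development of T1DM".

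**The concern.** The two definitions disagree about a child with one confirmed positive, negative samples afterwards, and diabetes later. The introductory summary does not count that child as an autoimmunity event; 9.1 does, provided criterion c is met where it applies. The first primary outcome is then partly decided by the second.

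Two consequences follow for the planned analyses.

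- **Ascertainment.** Two children with the same antibody history can differ on the first endpoint because diabetes was found in one and missed in the other. Section 10.8 relies on diabetes surveillance for children who leave the study, but names sources for only four sites: Colorado, part of Washington, Finland and Sweden.
- **Risk sets.** Section 10.1 censors children when last known event-free and draws controls by incidence density sampling. If the event is dated to the first positive, a child already drawn as an event-free control could become a case from a date before the draw. Section 10.1 foresees controls who convert later, but not this.

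A factor that affects only diabetes could then appear, diluted, as a factor for autoimmunity.

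**Working it through.** **1. Comparing the texts.** Take one child: confirmed positive at age 2, negative on every later sample, diabetes at 13.

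- Introduction, outcome measures: there is no second consecutive confirmed visit, so no event.
- 9.1, criterion b: diabetes has been diagnosed, no window applies, and nothing excludes intervening negatives. Criterion b is met.
- 9.1, transient class: follow-up is negative but diabetes has developed, so the child is not transient.
- 8.2.1 and 8.12.4.3.1: not persistent.

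The transient class applies the no-diabetes condition to children who were retested and found negative; the never-retested have their own class. So the wording does not confine diabetes to replacing a sample that could not be drawn.

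**2. The plan's own counts.** Section 10.3 projects 7,013 general-population children and 788 relatives, with 4% and 13.3% autoimmune conversion by age 6.

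- 7,013 × 0.04 = 280.5 (stated: 281)
- 788 × 0.133 = 104.8 (stated: 105)
- Total of the stated counts: 386

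The same counts are projected for diabetes by age 15: 386 / 7,801 = 4.9%.

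**3. Children who change status.** The protocol gives neither the number of transient positives nor their diabetes risk. Assume that 1% to 3% of 7,801 are transient, which is 78 to 234 children.

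- At the cohort risk of 4.9%: 78 × 0.049 = 4 to 234 × 0.049 = 12
- At four times that risk, 19.6%: 78 × 0.196 = 15 to 234 × 0.196 = 46

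A second set of assumptions takes transient positives as 10% to 50% of 386, with 2% to 20% of them later diabetic. It gives 386 × 0.10 × 0.02 = 1 to 386 × 0.50 × 0.20 = 39 children.

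**4. Denominator.** Diabetes reclassification runs to age 15, so the matching event count is also to age 15. If conversion is exponential, which 10.2.3 assumes for diabetes:

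- General population: 1 − 0.96^(15/6) = 9.7%; 7,013 × 0.097 = about 680
- Relatives: 1 − 0.867^(15/6) = 30.0%; 788 × 0.300 = about 237
- Total: about 917

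Sections 8.11 and 8.12.1.2 report declining seroconversion at older ages, so the true count probably lies between 386 and 917.

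**5. Size of bias.** Take a factor with hazard ratio 2 on diabetes and 1 on autoimmunity, exposure 10%, and s the share of reclassified events. Approximately, HR = (1 − s) × 1 + s × 2 = 1 + s. The yardstick, chosen here and not taken from the protocol, is half a standard error of log HR, 0.5 / √(D × 0.1 × 0.9), where D is the number of events.

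| Events D | Worst-case s | HR | log HR | Half SE |
|---|---|---|---|---|
| 386 (by age 6) | 46/386 = 12% | 1.12 | 0.113 | 0.085 |
| 917 (by age 15) | 46/917 = 5% | 1.05 | 0.049 | 0.055 |

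Adding the reclassified children to the smaller denominator gives 46/432 = 11% and log HR 0.10, still above 0.085. On events to age 15, the worst case falls below the yardstick.

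**The case against.** The best defence is that diabetes is meant only to stand in for the next sample. Criterion b sets it beside that sample, the lead-in speaks of antibodies on subsequent samples, and 9.1 says it errs toward strictness. Under 9.2.1, diagnosis leads to a final visit, so routine sampling ends and a substitute is needed. The transient class can also be read as merely the complement of b. This makes the narrow reading a plausible intention, but it is not what is written: the no-diabetes condition is attached to children who were retested and negative.

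A second defence is that diabetes reasonably corroborates a confirmed antibody, and that a short summary line need not repeat the full definition. Such a case definition is defensible, but then the summary, the time limit and the event date should say so.

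Three further objections stand.

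- 9.1 gives no dating rule. Dating to the first positive is an inference from the reference to first appearance, and the control-sampling problem depends on it.
- Any persistence endpoint dated to its first sample looks ahead. The proposed wording shortens the look-ahead to one visit interval but does not remove it.
- The surveillance sources in 10.8 would find diabetes in some children who drop out, so a lost child does not always stay transient.

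The schema in 9.1 could not be read in the copy available. If it contains a window or a criterion d, the text should be aligned with it.

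**Conclusion.** The inconsistency in a primary endpoint definition is real. As written, 9.1 lets later diabetes, and whether it is ascertained, decide whether a child with one confirmed positive and later negatives is an autoimmunity event.

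A reader might infer that the protocol expressly back-dates such events, or that the autoimmunity hazard ratios will be materially distorted. The documents support neither. The open-ended time limit follows from the absence of a window, and the event date is simply not stated. The number of children affected is unknown. On the assumed inputs (1% to 3% transient, diabetes risk from the cohort average to four times it), the upper end is about 5% of events to age 15, or about 12% of the 386 by age 6. The bias is probably small, and it exceeds half a standard error only at the upper end with the smaller denominator.

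This is a low-severity point. It is worth correcting because it concerns a primary endpoint and the change is cheap.

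**What to change.** - In 9.1, limit the diabetes alternative in criterion b to diabetes diagnosed before the next sequential serum sample is drawn.
- Classify a child whose next sample is negative as transient for that episode, whatever follows. A later persistent episode counts from its own date, and later diabetes counts in the second primary outcome.
- State the date assigned to the event.
- Bring the outcome measures in the Introduction and both parts of 9.1 into line with this wording.
- Amend the statement in 10.1 that diabetes cases are a subset of autoimmunity cases. Section 9.2 already allows for diabetes without an identifiable antibody-positive period.
- Remove the reference to criterion d, or restore the criterion if one was dropped.

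The cost is protocol wording and reclassification of a few children. There would be a handful fewer autoimmunity events, and some diabetes cases would no longer be autoimmunity cases, so they would need their own controls. No diabetes case is lost from the second outcome.

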## 9.2. Diabetes

The second primary outcome of the TEDDY study will be the development of T1DM. Diabetes will be defined using the ADA Expert committee classification (Expert Committee on the Diagnosis of Diabetes Mellitus, 1997). This classification is based on pathogenesis rather than the requirement for insulin therapy.

The most common form of childhood diabetes is type 1A diabetes, caused by the autoimmune destruction of pancreatic islet beta cells leading to an absolute deficiency of insulin and marked by the presence of at least one of the islet autoantibodies described in the previous section. It is expected that by age 15 years, type 1A diabetes will develop in up to 380 children enrolled in the TEDDY follow-up study.

The HLA eligibility criteria and family history of type 1 diabetes make it unlikely that other forms of diabetes will be observed. However, it is possible that some children will progress to diabetes without an identifiable period of islet autoantibody positivity.

Recently, increased numbers of children with diabetes presenting with clinical characteristics of type 2 diabetes (typically considered a disease of adults) have been reported, especially in minority populations (American Diabetes Association, 2000). Other categories of specific disorders, (onset usually during childhood) include mitochondrial mutations and various forms of Maturity Onset Diabetes of Youth (MODY), characterized by mild to severe insulin deficiency (Hattersley, 2000;Owen et al., 2003). In addition, a form of diabetes termed "atypical diabetes mellitus in adolescents" is being reported to occur in approximately 10% of African Americans and is associated with episodes of ketoacidosis followed by disease remissions where insulin therapy is not required to prevent ketoacidosis (Winter et al., 1987).

The issue of "double diabetes", i.e. coexistence of islet autoimmunity, insulin resistance and beta cell failure will likely be more important in TEDDY population than rare forms of diabetes, such as MODY. While presence of islet autoantibodies in TEDDY participants diagnosed with diabetes will be sufficient to classify those cases as type 1A diabetes, markers of insulin resistance (e.g., higher BMI, higher fasting insulin or C-peptide levels or HOMA (Matthews et al., 1985) will have to be included as potential confounders in the analyses of time to progression to diabetes. The "Accelerator Hypothesis" (Wilkin, 2001) argues that autoimmune destruction of beta cells is accelerated by weight gain and insulin resistance, thus type 1A diabetes may develop faster in children who are overweight. In addition, some suggested that higher BMI may be associated with increased prevalence and titer of islet autoantibodies, especially GAD (Weets et al., 2001; Rolandsson et al., 1999).

To diagnose diabetes, the following ADA Criteria must be met on two occasions (unless criteria 4 is present):

- 1. Casual (any time of day without regard to time since last meal) plasma glucose >= 200 mg/dL, if accompanied by unequivocal symptoms (i.e. polyuria, polydipsia, polyphagia, and/or weight loss.)
- Or

2. Fasting (no caloric intake for at least 8 hours) plasma glucose  $\ge 126 \text{ mg/dL}$ Or

- 3. 2-hour plasma glucose >=200 mg./dL oral glucose tolerance test (OGTT). Glucose dose is determinant on body weight to a maximum of 75 grams.
- Or
- 4. Unequivocal hyperglycemia with acute metabolic decompensation (i.e. ketoacidosis)

Unless criterion 4 is present or the fasting glucose is >=250 mg/dL (at the bedside or in the local laboratory on the day of testing), it is preferred that at least one of the two testing occasions involve an oral glucose tolerance test (OGTT). If the first criterion met is #3, i.e. by the 2-hour OGTT value, the OGTT should be repeated within 60 days. It is essential that every effort be made to obtain the necessary tests to establish the diagnosis of diabetes. Subjects will be instructed to eat a balanced diet in the days leading up to the OGTT.

